#### **3.4.4 Exclusion Criteria (Control Subjects)**

- (1) Previous adenotonsillectomy
- (2) Previous use of CPAP
- (3) Craniofacial anomalies that can interfere with upper airway anatomy (e.g., Treacher-Collins syndrome)
- (4) Genetic syndromes (e.g., Trisomy 21, Prader-Willi)
- (5) ADHD on medication
- (6) Developmental delay as determined by receiving a score  $<70$  on the ABAS-III.
- (7) Positive Pediatric Sleep Questionnaire
- (8) Non-English speaking participants due to the nature of neurobehavioral testing

---

## 4 STUDY PROCEDURES

### 4.1 OSAS Participants

#### 4.1.1 Screening Visit + Visit 1

The following procedures will be performed:

- Informed consent will be obtained before any study procedure/evaluations occur
- Review of inclusion/exclusion criteria
- Administer ABAS-III
- Demographics and medical history
- Mallampati/tonsillar size assessment
- Height and weight assessment
- OSAS participants will undergo a sleep study only if this has not been obtained clinically during the previous 12 months.
- OSAS participants will undergo a sleep study with CBF testing if a diagnostic sleep study has already been performed to confirm OSAS.

#### 4.1.2 Visit 2: Daytime, 1 to 30 days after screening visit

- Mallampati airway score and tonsillar assessment
- Cognitive and behavioral testing
- CBF testing during wakefulness during hypercapneic ventilatory response

#### 4.1.3 Visit 3: Post-Operative sleep study 6-12 weeks after adenotonsillectomy

- Sleep study to assess resolution of OSAS. If the post-operative AHI is  $\geq 5$  events per hour, participants will be referred to clinical care. However, they will continue in the study and perform procedures as planned. Data collected from such participants will be analyzed separately.
- Height and weight assessment.

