### **3.4 Study Population**

#### **3.4.1 Inclusion Criteria (OSAS subjects)**

Subjects with OSAS who fulfill the following clinical and polysomnographic criteria will be included:

---

- (1) Age between 6 years and 12 years. The lower limit criterion was selected to include children who can understand and cooperate with testing. The upper limit criterion was selected to avoid overlap with the adult presentation of OSAS.
- (2) Absence of neurologic, cardiovascular, pulmonary, or any other chronic illness with the exception of well-controlled asthma
- (3) No prior surgery on the nose, palate or oropharynx including an adenotonsillectomy
- (4) No current drug intake that may interfere with testing such as sedatives or stimulants
- (5) No prior treatment of sleep-disordered breathing
- (6) Polysomnographic recording criteria: subjects with OSAS must have an obstructive apnea hypopnea index (AHI)  $\geq 5/\text{hour}$  and be a candidate for clinically-indicated surgical treatment.
- (7) Parental/guardian permission (informed consent) and if appropriate, child assent.

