#### **3.4.3 Inclusion Criteria (Control subjects)**

Control subjects who fulfill the following clinical and polysomnographic criteria will be included:

- (1) Age between 6 years and 12 years. The lower limit criterion was selected to include children who can understand and cooperate with testing. The upper limit criterion was selected to avoid overlap with the adult presentation of OSAS.

---

- (2) Absence of neurologic, cardiovascular, pulmonary, or any other chronic illness with the exception of well-controlled asthma
- (3) No prior surgery on the nose, palate or oropharynx including an adenotonsillectomy
- (4) No current drug intake that may interfere with testing such as sedatives or stimulants
- (5) No prior treatment of sleep-disordered breathing
- (6) Polysomnographic recording criteria: Normal control subjects must have an AHI  $\leq$  1.5/hour.
- (7) Parental/guardian permission (informed consent) and if appropriate, child assent.

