#### 6.4.2 Analysis of Primary Outcome of Interest

The primary analysis will include all subjects meeting all inclusion and exclusion criteria and completing all study visits.

The primary endpoint will be the change in CBF in OSAS and controls at baseline.

The secondary endpoint will be the change in CBF in OSAS and controls at 6 and 12 months after baseline measurements for controls and after adenotonsillectomy for OSAS.

Longitudinal models using generalized estimating equations (GEE) will be fitted to explore effects of treatment on CBF and NBT. An indicator variable for treatment, time, and a time by treatment group interaction term will be included in the models. If the interaction term

---

differs significantly from zero, this will indicate that the change over time in the outcome of interest differs significantly between the two groups. We will assess the sensitivity of results to the choice of working correlation structure that models association in the GEE analyses. We will also implement quasi-least squares (QLS), an approach based on GEE that allows for implementation of the Markov correlation structure.(32) The Markov structure is plausible if participants have unequal temporal spacing of their measurements. In addition, we will consider the application of mixed effects models if the assumptions of these models are met. An indicator variable for subjects who resolve after treatment versus those who do not resolve after treatment will be included in the model to account for those children whose OSAS may not resolve after surgery.(22, 33, 34) Pre-, post treatment change in AHI will be included in the model, and potential confounding variables such as age, gender, race, socio-economic status and BMI will also be included in the models.

Hypercapnic ventilatory responses will be controlled for BMI as obese participants may have different responses compared to non-obese participants.

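### Sections 4.1.3 and 6.4.2 handle children whose OSAS persists after surgery in two different ways, and following 4.1.3 would answer the before/after objective in children selected on treatment response

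*Combined protocol and SAP*

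**What the plan says.** Section 4.1.3 describes Visit 3, 6-12 weeks after surgery, as a "Sleep study to assess resolution of OSAS". Its only threshold is an AHI of 5/hour or more. Children at or above it are referred for clinical care and continue all study procedures, and "Data collected from such participants will be analyzed separately".

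Section 6.4.2 takes another route. It fits longitudinal GEE models with treatment group, time and their interaction, and adds an indicator of whether OSAS resolved, "to account for those children whose OSAS may not resolve after surgery". The pre- to post-treatment change in AHI is a further covariate. The only analysis set stated there is the one for the primary analysis: all subjects who meet the entry criteria and complete all visits. It makes no exception for persistent disease. The section does not mention a separate analysis and does not say what AHI counts as resolved.

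The analyses at stake are secondary. Section 2.2 asks whether CBF regulation, cognition and behaviour improve after treatment. Section 6.2 lists the before/after changes as secondary endpoints. Section 6.4.2 places the primary endpoint at baseline.

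**The concern.** One section sets a group of operated children aside and the other models them together with the rest. An analyst could follow either and claim to have kept to the plan, and the choice could be made after the post-treatment data are seen.

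The choice matters because post-operative AHI is a result of treatment. An estimate of change after treatment restricted to children below the cut describes responders, not the children who had surgery. If non-responders improve less in CBF response or cognition, that estimate is too favourable for the question in section 2.2.

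The joint model does not fully remove the problem. The resolution indicator and the AHI change are both measured after surgery, so a treatment-by-time term adjusted for them is no longer the overall change in operated children. With no cut for the indicator, the model also cannot be reproduced from the text.

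**Working it through.** **1. The plan's own figure.** Section 6.5 gives 50 per group, effect size 0.566, two-sided alpha 0.05 and 80% power. A noncentral-t calculation gives 80.0% power at 50 per group (required n 49.98), so the figure reproduces. It concerns a two-group comparison, and the primary one is at baseline. The present point does not change it.

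**2. The two rules side by side.**

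| | Section 4.1.3 | Section 6.4.2 |
|---|---|---|
| Children with persistent OSAS | analysed apart | in the same model, with an indicator |
| Sample for the main before/after estimate | not stated; on a literal reading, post-operative AHI below 5 | only stated set: all eligible completers |
| Cut | AHI 5/hour or more | none given |
| Partial response | not addressed | AHI change as covariate |

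Both rules cannot describe the same main analysis.

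**3. Size of the selection effect.** The documents give no failure rate and no expected change in SD units, so these inputs are assumptions:
- q, the share with persistent OSAS: 10% to 40%
- g, mean improvement in non-resolvers: 0.1 to 0.3 SD
- mean improvement in resolvers: 0.5 SD

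Mean in all operated children = (1 - q) x 0.5 + q x g.

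| q | g = 0.1 | g = 0.3 |
|---|---|---|
| 10% | 0.45 + 0.01 = 0.46 | 0.45 + 0.03 = 0.48 |
| 40% | 0.30 + 0.04 = 0.34 | 0.30 + 0.12 = 0.42 |

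The analysis restricted to resolvers reports 0.50 SD in every case. The overstatement is q x (0.5 - g). It runs from 0.10 x 0.2 = 0.02 SD to 0.40 x 0.4 = 0.16 SD, and is zero if both groups improve equally.

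**4. Size of the set-aside group.** With about 50 evaluable OSAS children (section 3.2), 10-40% is 5 to 20 children, too few for a stable analysis on their own.

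**5. The available cut.** The Visit 3 value of 5 equals the OSAS entry value in section 3.4.1 (5/5 = 1.0). Section 3.4.3 says "Normal control subjects must have an AHI" of at most 1.5/hour, and 5/1.5 = 3.3. Children above 1.5 and below 5 after surgery would meet neither group's AHI criterion.

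**The case against.** The best defence is that the separate analysis is an added subgroup look and that section 6.4.2 governs. Section 6.2 defines the endpoints in OSAS subjects before and after treatment, section 4.1.3 keeps these children in the study, and the stated analysis set does not remove them. On that reading the analysis wanted here is already close to the plan. This is a fair reading, and for that reason the overstatement is conditional. But neither section says that the separate analysis is additional, and the indicator remains undefined.

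It is also fair that the AHI-change covariate represents partial response on a continuous scale. A child who moves from 5.2 to 4.8 enters with a change of 0.4, not only as a yes or no. That softens the classification problem inside the model. It does not define the indicator, and it does not give the unconditional before/after change.

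A reader might go further and infer that any child below 5 counts as resolved, so that partial response or night-to-night variation passes for cure. The documents do not support this. They attach 5 to referral and separate analysis and never state that a lower value means resolved. The 1.5 limit is an eligibility rule for controls, not a definition of cure. No night-to-night variability is given, so any rate of misclassification would rest on assumed inputs.

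**Conclusion.** The conflict between sections 4.1.3 and 6.4.2 is real, and so is the missing definition of resolution. Both should be settled before post-treatment data are analysed. If section 4.1.3 is followed, the before/after result comes from children selected on response. Under the assumed ranges it would read 0.50 SD where all operated children average 0.34-0.48 SD. The direction depends on non-resolvers improving less, and the size cannot be known from the documents.

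The effect is limited to the secondary post-treatment analyses. A reader might infer that these children's baseline data also leave the primary comparison. The documents do not support that: the primary set in section 6.4.2 depends on eligibility and visit completion, not on post-operative AHI.

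**What to change.** For analysis only, with the referral rule left as it is:

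1. In section 4.1.3, replace the sentence on separate analysis with a statement that these children stay in the main longitudinal analysis.
2. In section 6.4.2, state that the before/after change in CBF, cognition and behaviour is estimated first in all operated OSAS children, without the resolution indicator or the AHI change in the model. Analyses by resolution status and by AHI change follow as a second step.
3. Fix in advance the Visit 3 AHI cut that defines the indicator.
4. Because the only cut given equals the entry value and is 3.3 times the control limit, add a sensitivity analysis using continuous Visit 3 AHI or the trial's own 1.5 limit. A compulsory split into three AHI groups is not needed; with about 50 children the cells could be very small.

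The cost is a few sentences in two sections. No new visits or data are needed, because the Visit 3 study is already scheduled. The downside is a possibly less favourable headline change and small subgroups in the second step.

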#### 4.1.4 Visit 4: Daytime, 6 months after adenotonsillectomy

- Cognitive and behavioral testing
- CBF testing during wakefulness during hypercapneic ventilatory response

#### 4.1.5 Visit 5: Nighttime, 6 months after adenotonsillectomy

- CBF testing during sleep during hypercapneic ventilatory response

- Height and weight assessment

**4.1.6 Visit 6: Daytime, 12 months after adenotonsillectomy**

- Cognitive and behavioral testing
- CBF testing during wakefulness during hypercapneic ventilatory response

**4.1.7 Visit 7: Nighttime, 12 months after adenotonsillectomy**

- CBF testing during sleep during hypercapneic ventilatory response
- Height and weight assessment

**4.2 Control Participants****4.2.1 Screening Visit (Visit 1)**

- Informed consent will be obtained before any study procedure/evaluations occur
- Review of inclusion/exclusion criteria
- Administer ABAS-III
- Demographics and medical history
- Height/weight assessment Baseline sleep study to rule out OSA

**4.2.2 Visit 2: Daytime, 1 to 30 days after screening visit**

- Mallampati airway score and tonsillar assessment
- Cognitive and behavioral testing
- CBF testing during wakefulness during hypercapneic ventilatory response

**4.2.3 Visit 3: Nighttime, 1 to 30 days after screening visit**

- Height/weight assessment
- CBF testing during sleep during hypercapneic ventilatory response

**4.2.4 Visit 4: Daytime, 6 months after Visit 1**

- Cognitive and behavioral testing
- CBF testing during wakefulness during hypercapneic ventilatory response

**4.2.5 Visit 5: Nighttime, 6 months after Visit 2**

- Height/weight assessment
- CBF testing during sleep during hypercapnic ventilatory response

---

**4.2.6 Visit 6: daytime, 12 months after Visit 1**

- Cognitive and behavioral testing
- CBF testing during wakefulness during hypercapneic ventilatory response

**4.2.7 Visit 7 Nighttime, 12 months after Visit 1**

- Height/weight assessment
- CBF testing during sleep during hypercapnic ventilatory response

**4.3 Monthly Telephone Calls**

- There will be telephone calls during each month that a visit into the hospital is not necessary (months 2, 3, 4, 5, 7, 8, 9, 10, 11) for retention purposes, as well as to assess for adverse events.

**4.4 Unscheduled Visits**

Occasionally, due to technical issues arising from the complex set up necessary for NIRS data collection, the data may not be optimal. Therefore, we will need to recollect CBF data during wakefulness from some subjects. In these cases, we will contact them asking their permission to be retested. Those who agree will be re-consented and receive the standard stipend for the daytime testing.

**4.5 Subject Completion/Withdrawal**

Subjects may withdraw from the study at any time without prejudice to their care. They may also be discontinued from the study at the discretion of the Investigator for lack of adherence to study treatment or visit schedules, AEs, or due to inability to follow instructions and perform testing. The Investigator or the Sponsor (if applicable) may also withdraw subjects who violate the study plan, or to protect the subject for reasons of safety or for administrative reasons. It will be documented whether or not each subject completes the clinical study. If the Investigator becomes aware of any serious, related adverse events after the subject completes or withdraws from the study, they will be recorded in the source documents and on the CRF.

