## ABSTRACT

Context:

- Children with the obstructive sleep apnea syndrome (OSAS) have impaired behavior and cognition compared to normal controls.
- OSAS is characterized by repetitive occlusion of the upper airway during sleep that results in hypoxemia, hypercapnia and arousal from sleep.
- Previous studies in adults with OSAS have shown significant alterations of cerebral blood flow during wakefulness and sleep and our preliminary data showed blunted cerebral blood flow response to hypercapnia in children with OSAS during wakefulness. However, it is unknown whether children with OSAS also have impaired cerebral blood flow during sleep.
- It is unknown whether the deficits in behavior and cognition in children are associated with cerebral blood flow dysregulation.
- We hypothesize that children with OSAS have an impaired cerebral blood flow during wakefulness and sleep as compared to normal controls. We further hypothesize that the degree of this impairment will correlate with neurocognitive function.

Objectives:

- To investigate whether the changes in cerebral blood flow during wakefulness and sleep elicited by hypercapnic challenge, differ in children with OSAS compared to normal controls.
- To investigate the changes in cerebral blood flow during wakefulness and sleep elicited by hypercapnic challenge in children with OSAS before and after treatment (adenotonsillectomy, adenoidectomy, or tonsillectomy).
- To investigate whether the changes in cerebral blood flow elicited by the aforementioned testing correlate with neurocognitive outcomes.

Study Design: Case-control study

Setting/Participants:

- Children's Hospital of Philadelphia, Pulmonary Division, outpatient offices
- Children with OSAS aged 6-12 years will be recruited following a clinical polysomnogram. Normal age- and gender-matched controls will be recruited from the general community.

Study Interventions and Measures:

- The following procedures will be performed in OSAS subjects pre- and post- adenotonsillectomy, and controls:

---

- Sleep study at baseline, 6 and 12 months. For OSAS participants, there will be an additional sleep study 6-12 week post clinically indicated surgical treatment to assess resolution of OSAS.
- Neurocognitive testing at baseline, 6 and 12 months for controls
- Neurocognitive testing at baseline, and 6 and 12 months after clinically indicated surgical treatment of OSAS for children with OSAS

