**4.5.1 Early Termination Study Visit**

Subjects who withdraw from the study will be referred for clinical care.

**5 STUDY EVALUATIONS AND MEASUREMENTS****5.1 Screening and Monitoring Evaluations and Measurements****5.1.1 Medical Record Review**

The following procedures will be performed:

- Demographics: age, gender, race

---

- Review of inclusion/exclusion criteria
- Previous PSG, if available.

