    - Digit Span subtest of the Wechsler Intelligence Scale for Children, 4th Edition.
    - Tests of Everyday Attention for Children (TEA-ch)
    - Purdue Pegboard Test
    - Behavioral Rating Inventory of Executive Function -- Child Version (BRIEF-2)
    - Child Behavior Checklist
    - Epworth Sleepiness Scale Modified for Children
    - Adaptive Behavior Assessment System, Third Edition (ABAS-III)

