### 6.3 Control of Bias and Confounding

The co-investigator performing the neurocognitive testing will be blinded to the subjects' condition (OSAS or controls).

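### Section 4.5 allows a child to be discontinued from the whole study for being unable to do the tests, and 6.4.2 then drops that child's baseline CBF data; if this happens more often in OSAS, the CBF comparison and the CBF-cognition correlation may be attenuated

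*Combined protocol and SAP*

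**What the plan says.** Section 4.5 (Subject Completion/Withdrawal) says of participants in general: "They may also be discontinued from the study at the discretion of the Investigator". The grounds are "lack of adherence to study treatment or visit schedules, AEs, or due to inability to follow instructions and perform testing". No threshold, number of attempts or procedure is given. On documentation the section says: "It will be documented whether or not each subject completes the clinical study". It does not ask for the reason. Section 4.5.1 is titled as an early termination visit, but its whole content is: "Subjects who withdraw from the study will be referred for clinical care".

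The outcomes include tests of attention, motor speed and working memory and parent-rated behaviour scales (5.1.3). Section 6.1 makes their correlation with the CBF response part of the primary endpoint. The Abstract gives the premise: "Children with the obstructive sleep apnea syndrome (OSAS) have impaired behavior and cognition compared to normal controls".

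Section 6.4.2 places the primary endpoint at baseline and defines the analysis set: "The primary analysis will include all subjects meeting all inclusion and exclusion criteria and completing all study visits".

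Section 3.1 describes a prospective case-control study. Under 3.4.1 the OSAS children are candidates for surgery that is clinically indicated, and controls have no treatment. Section 6.3 states blinding only for the person who does the neurocognitive testing.

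**The concern.** Being unable to follow instructions or complete a test is close to what the cognitive battery measures. A rule that removes a child from the whole study on that ground can therefore select on the outcome. It also gives up data the child could still provide, such as the sleep CBF challenge, the parent-rated scales, the sleep studies and later visits.

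The completers-only rule in 6.4.2 extends the damage to the primary endpoint. Without it, a child discontinued after baseline would still count in the baseline comparison. With it, a failure at month 6 or 12 deletes a baseline CBF measurement that was already usable.

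The *study treatment* ground has no clear meaning here. Nothing is assigned by the study, and on the natural reading (surgery) it could apply only to OSAS children.

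If removals are commoner in OSAS, and poorer performers also have the more blunted CBF response, the group CBF difference shrinks and the range available for the correlation narrows. Because only completion status is documented, the pattern might not be recoverable afterwards.

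**Working it through.** **1. The plan's own figure.** Inputs from 6.5: effect size 0.566, two-sided alpha 0.05, 50 per group. The noncentral-t power is 80.0%, so the stated figure reproduces. Recruiting 70 per group matches 50/(1 - 20/70), an allowance of 28.6%. Neither the reasons for attrition nor its split by arm is given. The sample size is not in error.

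**2. What follows from the text alone.** 4.5 permits removal from the study for test failure. 6.4.2 excludes anyone who misses a later visit. 6.4.2 also puts the primary endpoint at baseline. Together, a removal after baseline deletes baseline data. This needs no assumption.

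**3. Illustration of selection on cognition.** The documents give no removal rate and no cognitive effect size. Assumptions:
- performance is normal with SD 1 in each group;
- the true gap is g = 0.566 SD. This borrows the planning effect size, which the Synopsis attaches to CBF changes, so it is not a documented cognitive deficit;
- one cut-off applies to both groups and removes a fraction c of controls.

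Let a be the standard normal quantile of c, b = a + g, λ(x) = φ(x)/(1 - Φ(x)) and V(x) = 1 + xλ(x) - λ(x)².
- OSAS fraction removed = Φ(b)
- remaining gap, in SD before selection = g - λ(b) + λ(a)
- standardised gap = remaining gap / √[(V(a) + V(b))/2]

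| c | a | b | OSAS removed | λ(a) | λ(b) | Remaining gap | Pooled SD | Standardised gap | Loss |
|---|---|---|---|---|---|---|---|---|---|
| 2% | -2.054 | -1.488 | 6.8% | 0.049 | 0.142 | 0.474 | 0.913 | 0.519 | 8% |
| 3% | -1.881 | -1.315 | 9.4% | 0.070 | 0.186 | 0.451 | 0.890 | 0.506 | 11% |
| 5% | -1.645 | -1.079 | 14.0% | 0.109 | 0.259 | 0.415 | 0.855 | 0.486 | 14% |

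In pre-selection SD units the loss is 16-27% (0.474/0.566 to 0.415/0.566). That overstates the loss as an effect size, because truncation also shrinks the SD.

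Of 70 recruited per group, these rates are 1.4 to 3.5 controls and 4.8 to 9.8 OSAS children, which is within the 20 per group allowed for.

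Sensitivity to g at c = 5%: for g = 0.3, 0.5 and 0.8, OSAS removal is 8.9%, 12.6% and 19.9%, and the standardised gap falls by 12%, 14% and 16%. With g = 0 removal is equal and nothing shifts.

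**4. Carry-over to the CBF endpoint.** This needs a further assumption, a within-group correlation ρ between performance and CBF response. With g = 0.566 and c = 5%, the shift is ρ[λ(b) - λ(a)].
- For ρ = 0.3: 0.3 × (0.2593 - 0.1086) = 0.045, and 0.566 - 0.045 = 0.521.
- V(a) = 0.810 and V(b) = 0.653, mean 0.731, so the CBF SD becomes √(1 - 0.09 × 0.269) = 0.988. The standardised difference is 0.521/0.988 = 0.527, and power at 50 per group is 74%.
- The correlation within OSAS becomes ρ√V(b)/√(ρ²V(b) + 1 - ρ²) = 0.25 instead of 0.30.
- For ρ = 0.2 and 0.5 the standardised difference is 0.539 and 0.508, and power is 76% and 71%. With ρ = 0 there is no shift.

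**5. What the analysis set costs.** If all 70 per group had usable baseline CBF and were analysed, power at 0.566 would be 91%, against 80% with 50 completers. This is an upper bound.

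**The case against.** A reader might infer that the clause removes the children with the worst attention, mostly from the OSAS arm. The documents do not support that as a statement of fact. The rule is permissive, applies to both groups, and comes with no rate. Inability to perform testing is not an attention score. It also covers the mouthpiece rebreathing test and the mask challenge during sleep, where age or intolerance may be the cause. A fixed cut-off in both groups is a hard reading of a discretionary clause. These points stand, and they limit the conclusion to a conditional one.

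Mitigations exist. The lower age limit was chosen for cooperation, medicated ADHD and ABAS-III below 70 are excluded in both groups, and breaks are offered. Failed rebreathing tests are discarded one at a time, waking CBF can be recollected (4.4), and children with residual OSAS stay in (4.1.3). They thin the lower tail without emptying it. The last three also show that the protocol already handles failure at test level, so removal from the study is not needed.

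A reader might also infer from 4.5.1 that nothing is collected after discontinuation. That is too strong, since 4.5 still records serious related adverse events that become known. No outcome assessment at exit is specified, however.

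Two further objections stand in part. A baseline group difference in cognition is not a listed endpoint, so the illustration in step 3 shows the mechanism and does not measure bias in the primary result. And OSAS visits 3 to 7 are timed from surgery, so deleting the *study treatment* ground keeps few visits for a child who has no operation. That part is mainly a matter of wording.

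**Conclusion.** The concern holds in conditional form. It is established by the text that 4.5 allows removal from the whole study on a ground that overlaps with the outcomes, that the reason need not be recorded, that *study treatment* has no referent in 3.1 or 3.4.1, and that 6.4.2 turns any later removal into a loss of baseline CBF data.

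That removals would be commoner in OSAS is an expectation drawn from the protocol's premise. Its size is not known. Under the assumptions of step 3 the standardised cognitive gap is 8-14% too small. Under those of step 4 the CBF difference falls from 0.566 to about 0.51-0.54. Both vanish if the groups perform alike, and the CBF shift also vanishes if performance and CBF response are unrelated within groups.

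The change should be made. It is cheap, and data from children who have been removed cannot be recovered.

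**What to change.** - **4.5:** remove inability to perform testing as a ground for discontinuation from the study. Record the individual test as 'not done - unable' and keep the child for all other tests and visits, in both arms.
- **4.5 against 3.1 and 3.4.1:** delete *study treatment* or reconcile it with the observational design.
- **Case report form:** add a reason for discontinuation and a code for 'unable'. Report both by arm and visit.
- **6.4.2:** analyse the baseline primary endpoint in all eligible children with usable baseline CBF data, whether or not they complete later visits.

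The cost is wording in two sections and reason codes on the case report form. The visits retained are already in the schedule. Some visits will yield partial data, and cognitive scores coded 'unable' will still be missing. The change therefore reduces the selection without abolishing it, and makes what remains visible by arm.
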